2. TERMINOLOGY

2.1. Acronyms

BAP	Blood Agar Plate
bp	Base pairs
CDA	Confidentiality Disclosure Agreement
CDC	Centers for Disease Control and Prevention
CLIA	Clinical Laboratory Improvement Amendments
CRA	Clinical research associate
CTA	Clinical Trial Agreement
DNA	Deoxyribonucleic Acid
DTT	Disposable Transfer Tool
EC	External control
eCRF	Electronic Case Report Form
EDC	Electronic Data Capture
GBS	Group B Streptococcus
IEC	Independent Ethics Committee
INC	Inconclusive
IND	Indeterminate
IRB	Investigational Review Board
IUO	Investigational use only
NPV	Negative predictive value
PC	Process Control
PCR	Polymerase Chain Reaction
PI	Principal investigator
PPV	Positive predictive value
SB	Sample Buffer
SBT	Sample Buffer Tube
UNR	Unresolved

2.2. Definitions

Clinical Center(s)	The site(s) that will perform the GENEPOC GBS test and, the culture method for the clinical study.
GENEPOC GBS	Documents provided to investigators by GenePOC including the GenePOC instrument User's Manual, the GenePOC GBS Study Protocol, the GenePOC GBS Package Insert and the GenePOC GBS Study Site Manual.
GENEPOC GBS System	The system is composed of the GenePOC GBS test which is used in conjunction with the GenePOC™ instrument.
PCR Operator	Participating laboratory technician who has successfully completed the proficiency testing
PIE	GBS disposable microfluidic cartridges (describe in this document as PIE because of the shape of the cartridge).
Principal Investigator	Principal Investigator (PI): A person who actually conducts the clinical investigation, under whose immediate direction the test article (device) is used involving a sample derived from a human subject; or, in the event of an investigation conducted by a team of individuals, is the responsible leader of that team.
Reference Method	The Reference Method for this study will be the Culture, a culture method to detect Streptococcus agalactiae strain from a sample.
Sample	Left over Lim broth enrichment intended for regular culture.
Sponsor	GenePOC Inc.
(Patient) sample	Vaginal/rectal swab samples collected for routine laboratory testing from a pregnant woman suspected to be colonized with Streptococcus agalactiae (GBS).

3. INTRODUCTION

3.1. Protocol Scope

The purpose of this clinical investigation is to establish the performance characteristics of the GenePOC GBS system for its use in determining the presence of GBS in vaginal/rectal swab samples, after Lim Broth enrichment, from pregnant women. Sensitivity and Specificity will be established in comparison to the Reference Method. For this investigation the Reference Method will be Lim broth culture, subcultured onto blood agar plate (BAP), routine method for detection of GBS coming from vaginal/rectal swab samples. Up to four (4) selected sites will perform this clinical investigation.

3.2. Intended Use

The GenePOC GBS test performed on the GenePOC System is a qualitative in vitro diagnostic test designed to detect Group B Streptococcus (GBS) DNA from vaginal/rectal swabs from antepartum women following enrichment in Lim broth for 18-24 hours. The GenePOC GBS test utilizes automated sample preparation and real-time polymerase chain reaction (PCR) to detect a *cfb* gene sequence specific to the *Streptococcus agalactiae* genome. The GenePOC GBS test is indicated for the identification of antepartum GBS colonization and does not provide susceptibility results. Culture isolates are needed for performing susceptibility testing as recommended for penicillin-allergic women.

3.3. Device Description

The GenePOC GBS test will be performed using the GenePOC instrument. The GenePOC instrument, used in conjunction with appropriate reagents, is capable of automated lysis cells, dilution of nucleic acids from multiple sample types as well as automated amplification and detection of target nucleic acid sequences.

The GenePOC GBS Assay reagents kits consist of:

Components	Packaging
Sample Buffer Tube (SBT)	A 4.5ml tube containing 1ml of sample buffer
Disposable Transfer Tool	Plastic disposable transfer pipette for transferring inoculated sample buffer (SB) into the PIE.
GBS disposable microfluidic cartridges (PIE)	Fully integrated disposable microfluidic cartridge for detection of GBS.

3.4. Test Principle

The study population consists of vaginal/rectal swab samples from pregnant women at 35-37 weeks of gestation for whom GBS diagnostic procedures are indicated and ordered. After the sample is collected and transferred into the transport media (Amies or Stuart), it is transported to the laboratory and stored at the appropriate temperature for no more than 96 hours.

When ready for testing, the swab is placed into a culture tube with Lim Broth for 18-24 hours. After incubation, a 15 µL aliquot of the broth is used for detection of the presence of GBS. The aliquot of the broth is mixed with GenePOC Sample Buffer Tube Reagent (SBT) and then vortex for 5 seconds, 100 to 200 µL of the Sample-SBT mix is transferred to the GBS PIE using the disposable transfer pipette. GBS PIE is then transferred into the GenePOC System for fully integrated real time analysis.

The GenePOC GBS test includes reagents for the simultaneous detection of the target GBS DNA, a process control (PC) to monitor processing, amplification, and the absence of reaction inhibitors. The GBS primers and probe detect a target region of 190 base pairs (bp) of the *cfb* gene of *Streptococcus agalactiae*. The results are interpolated by the system from measured fluorescent signals and embedded calculation algorithms. Results may be viewed, be printed, transferred and/or stored by the user.

3.5. Clinical Benefits and Justification for the Use of a New Technology

The group B streptococcus (*Streptococcus agalactiae*, GBS) is a cocci gram-positive bacterium that is one of the main causes of neonatal mortality in developed countries. Neonatal infections caused by GBS are found in two forms^{1,2}, early or late onset. The early-onset infections occur during the 7 days following birth; they are the cause of approximately 80% of GBS infections in newborns with mortality rate of 5-20%³. The late onset infections occur between the first week and the seventh month of life. They are rarer and the mortality rate is lower. In the case of early-onset infections, GBS is transmitted during childbirth via the genital tract of the mother while for late onset infections, contamination is not necessarily via the mother⁴. Prolonged hospitalization and the use of expensive equipment is generally required for GBS infected newborn care. Survivors may also suffer permanent damage such as mental developmental delay or loss of vision.

Currently, the clinical guidelines of the Centers for Disease Control and Prevention⁵ and the Canadian Society of Obstetricians and Gynaecologists⁶ recommend the use of a GBS screening during pregnancy (antenpartum) combined with a treatment of antibiotics for prophylaxis during delivery (intrapartum) to all women detected GBS positive. This approach has reduced the incidence of perinatal GBS infections in North America⁷. Unfortunately, the presence of a vaginal colonization in pregnancy does not necessarily indicate the presence of a settlement at the time of delivery. Some women are treated when they are no longer carriers of GBS, while others are not, consequently they will be carrying GBS at the time of delivery.

A first version of a screening test by polymerase chain reaction (PCR) in the early 2000s has demonstrated the usefulness of a rapid detection of GBS⁸. This method however, was not fully integrated (independent lysis method of PCR system), unlike the GenePOC system, limiting its use to hospital laboratories.

The GenePOC GBS test is a step further in rapid detection of GBS by increasing the automation of the detection and simultaneously increasing the ease-of-use.

4. TRIAL OBJECTIVES

The objectives of this multi-center prospective clinical study are:

- To establish the performance characteristics of the GenePOC GBS System for its use in determining the presence of GBS in vaginal/rectal swab, after Lim Broth enrichment, samples from antepartum pregnant women. Sensitivity and specificity will be established in comparison to the Reference Method.
- To estimate the Positive and Negative Predictive Values (PPV and NPV) of the GenePOC GBS System.
- To estimate the rate of unresolved results for the GenePOC GBS System due to Sample Processing Control failure (Unresolved sample results).
- To estimate the rate of indeterminate results for the GenePOC GBS test due to an Instrument failure (Indeterminate sample results).
- To determine the reproducibility between sites of the GenePOC GBS System.

5. STUDY DESIGN

5.1. Clinical Investigation Requirements

Up to four (4) GenePOC GBS clinical centers will participate in the clinical study. Clinical centers will be selected for the clinical study based on a number of criteria, such as investigator and site personnel availability, number of samples of interest tested for GBS, GBS prevalence, familiarity with the study Reference Method, and experience with GBS culture isolation and clinical investigations.

Site(s) will have a laboratory where GBS characterization methods are performed for routine, investigation or research purposes. The exact same media type, reagents and procedure will be used for performing the Reference Method throughout the clinical investigation by all sites.

The Clinical investigation requirements relating to each Clinical Centers are detailed in Appendix A.

5.2. Overview of the Evaluation

The Clinical investigation will consist of four (4) distinct segments: Proficiency testing, Clinical Accuracy testing, Discrepant testing (optional) and Assay Reproducibility (selected sites).

5.2.1. Proficiency Testing

Each PCR operator who will participate in the GenePOC GBS clinical study will be trained by a GenePOC Study Manager (or CRA) on handling and performing the GenePOC GBS test according to the Investigational Use Only (IUO) Package insert, the Study Site Manual and the GenePOC System User's Manual.

A test panel containing negative samples and GBS positive samples will be used to assess each new participating technician proficiency with the protocol test methods. This panel will be provided in a sufficient number and will contain negative samples and GBS positive samples. A participating technician failing to achieve the qualification criteria on initial testing of the GenePOC GBS System must repeat the training panel (a maximum of two times), and will be qualified if he/she meets the acceptance criteria for the repeated runs. If the participating technician fails to meet the retest criteria, he/she cannot be qualified for participation in the GenePOC GBS clinical study as a PCR operator for the GenePOC GBS System unless re-training occurs and the participating technician is able to pass the proficiency test.

To be qualified for participation in the GenePOC GBS clinical study as a PCR operator, each participating technician must achieve a correct answer for all positive samples and true negative (no target) samples in the molecular method using the provided proficiency panel.

For the Reference Method no proficiency testing will be done.

If a new participating technician is included in the study after the initial training and proficiency testing occurs, the training of this person can be performed by a GenePOC representative or by a proficient PCR operator on-site. The new participating technician must also pass the proficiency test to participate in the study.

5.2.2. Clinical Accuracy Testing

This clinical study is designed in such a way that all sites may perform the Reference Method, which requires that each Clinical Center has laboratory facilities where GBS characterization methods are performed for routine, investigation or research purposes. Reference method is defined as Lim broth culture, subcultured onto blood agar plate (BAP) for detection of *Streptococcus agalactiae* strains. More specifically, the *Streptococcus agalactiae* bacteria, when present, will be isolated using an Enriched Culture method. The exact same media type, reagents and procedure will be used for performing the Reference Method throughout the clinical investigation by all sites.

To be considered for enrollment in the study, a sample must satisfy all eligibility criteria

described in Section 5.3 of this Protocol. Samples will be collected using a swab.

Sample testing will be performed according to Section 6 of this protocol. Results obtained from testing of samples using the GenePOC GBS System will be compared to those obtained by the Reference Method. These results will serve to verify the GenePOC GBS System performance.

GenePOC GBS System and Reference Method testing will be performed as described in the GenePOC GBS Investigation Documents and the testing algorithm shown in Appendix B. Investigators will ensure that, for a given sample, the PCR operator performing the test are masked from the results of the Reference Method and vice-versa.

The purpose of the clinical investigation is to enroll sufficient samples to obtain approximately 150 positives samples for GBS based on the Reference Method final result. With an estimated prevalence of approximately 25%, it is projected that up to 600 samples will be needed across all participating Clinical Centers.

The Study Manager will monitor sample enrollment and prevalence of GBS across all participating Clinical Centers. It may be necessary to increase the enrollment rate of samples or to prematurely stop enrollment at one or more participating centers, depending upon the total number of samples and the positive samples obtained across all Clinical Centers.

At least three (3) lots of the GenePOC GBS Assay kits will be used for this Clinical trial. Each Clinical Center will test a minimum of two (2) lots.

Once per day, a reference GBS strain bearing the *cfb* gene (e.g. American Type Culture Collection, ATCC 12973) will be used as a positive external control (EC) while not inoculated sample buffer will be used as a negative EC. If either or both of the ECs fail to give the expected result, all samples tested in that run will be repeated from the remaining SBT containing the sample stored at 2-8°C along with new positive and negative ECs.

5.2.3. Discrepant Testing (*optional*)

In cases of discrepant results between the Reference Method and the GenePOC GBS Assay, further characterization testing may be requested by GenePOC to be performed by the Clinical Center and possibly at GenePOC to attempt to resolve the discrepancy. See Section 6.3.3 and Appendix C for description of the minimal discrepant testing. An electronic or paper Discrepant Results Form will be used for recording discrepant testing information.

5.2.4. Assay Reproducibility Testing (*for selected sites*)

Reproducibility study will be performed with a panel of samples spiked at 4 different concentrations of GBS: Negative, High negative (1/50x LOD), Low positive (1.5x LOD), Moderate positive (3x LOD). Each panel will consist of 8 samples with 2 replicates of each concentration.

The site-to-site reproducibility will test the same reproducibility panel at three (3) designated sites (2 external sites and GenePOC laboratories) for the within-run (3 replicates), between-run (2 runs per day) and between-day (5 days, consecutive or not) variance with multiple operators and instruments. A single lot of the GenePOC GBS test will be tested by each sites according to the Study Site Manual instructions and the IUO GBS test Package Insert.

The reproducibility panel will contain randomized moderate positive, low positive and negative samples.

Once per day, a reference GBS strain bearing the *cfb* gene (e.g. ATCC 12973) will be used as a positive external control (EC) while not inoculated sample buffer will be used as a negative EC. If either or both of the ECs fail to give the expected result, all samples tested in that run will be repeated from the remaining SBT containing the sample stored at 2-8°C along with new positive and negative ECs.

5.3. Study Criteria

Note: For this study, samples will not be collected for the express purposes of this evaluation. Only excess de-identified samples will be used.

5.3.1. Inclusion Criteria

- Antepartum pregnant women
- 18 years old and more
- Being at a gestation period of 35 to 37 weeks.
- Vaginal/rectal swab sample
- Transport and storage times, and conditions (e.g. room temperature and/or refrigerated) within the labeled indications.
 - : If the sample will be processed within 24 hours, store at room temperature. If the sample will be tested after 24 hours, refrigerate until testing is performed. Sample stored at 2-8°C can be tested with the GenePOC GBS System
 - Fresh sample must be tested with the Reference Method within 96 hours (4 days) of collection if kept at 2-25°C
- The GenePOC GBS System and the Reference Method will be performed according to the GenePOC GBS Investigation Documents.
- Materials use within their expiration date

5.3.2. Exclusion Criteria

- Non pregnant women
- Less than 18 years old
- Gestation not between 35-37 weeks
- Transport and storage times and conditions that exceed these Study Protocol requirements
- The GenePOC GBS System and the Reference Method not performed according to the GenePOC GBS Investigation Documents
- Materials used beyond their expiration date
- Samples without all test results required by this Study Protocol. Samples that are inadvertently entered into the study that do not meet the sample inclusion criteria will be made non-compliant.

5.4. Sample Size Justification

The purpose of the clinical investigation is to enroll sufficient samples from up to four (4) Clinical Centers to obtain a minimum of 150 and a maximum of 160 samples positive for GBS based on the Reference Method final result. With an estimated prevalence of approximately 25%, up to 600 samples could be tested across all Clinical Centers.

A minimum of 30 positive results per site is expected but sites with a higher prevalence of GBS could contribute more positive results to reach the required number. A potential minimum of 200 samples and a potential maximum of 300 total samples will be obtained at each clinical center.

The performance obtained and the statistical confidence intervals will be monitored during the study in order to stop the enrollment when deemed appropriate.

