Reference Method	
Culture is defined as Lim broth culture, subcultured onto blood agar plate (BAP) for observation of a Streptococcus agalactiae strain. More specifically, the Streptococcus agalactiae bacteria, when present, will be isolated using an Enriched Culture and then identified by usual microbiological method.
 
The exact same media type, reagents and procedure will be used for performing the Reference Method throughout the clinical investigation by all sites.

------------------	---

Phase	Development Phase - Qualification of investigational device (IUO).
Planned Study Period	Clinical investigation to begin in January 2016 at the earliest and to be completed within approximately 8 weeks.
Planned Sample Size	The purpose of the clinical investigation is to enroll sufficient samples from four (4) Clinical Centers to obtain a total of 150 samples positive for GBS based on the Reference Method final result. With an estimated prevalence of approximately 25%, up to 600 samples will be tested across all Clinical Centers. The performance obtained and the confidence interval will be monitored during the study in order to stop the enrollment when appropriate. A minimum of 30 positive results per site is expected but sites with a higher prevalence of GBS could contribute with more positive results to reach the required number.
Objectives	
The primary objectives of this multi-center prospective investigational trial are:
 
• To establish the performance characteristics of the GenePOC GBS Assay for its use to detect Group B Streptococcus (GBS) DNA from Lim broth cultures. Sensitivity and specificity will be established in comparison to the Reference Method.• To estimate the Positive and Negative Predictive Values (PPV and NPV) of the GenePOC GBS Assay.• To estimate the rate of unresolved results for the GenePOC GBS Assay due to Sample Processing Control failure (Unresolved sample results).• To estimate the rate of indeterminate results for the GenePOC GBS Assay due to an Instrument failure (Indeterminate sample results).• To determine the reproducibility between sites of the GenePOC GBS System.

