Clinical Study Statistical Methods	
Results obtained with the GenePOC GBS System will be compared to those obtained with the Reference Method. The statistical analyses will include all compliant samples and will determine at least the following:
 
• The sensitivity and specificity, PPV and NPV as well as exact 95% confidence interval.• The unresolved and indeterminate rates along with 95% exact confidence interval.• Poolability of the data.• Reproducibility percent agreements for qualitative and quantitative data.

TABLE OF CONTENTS

1. INVESTIGATION CONTACTS	15
2. TERMINOLOGY	16
3. INTRODUCTION	18
3.1. Protocol Scope	18
3.2. Intended Use.....	18
3.3. Device Description.....	18
3.4. Test Principle.....	19
3.5. Clinical Benefits and Justification for the Use of a New Technology.....	19
4. TRIAL OBJECTIVES	20
5. STUDY DESIGN	20
5.1. Clinical Investigation Requirements	20
5.2. Overview of the Evaluation	21
5.3. Study Criteria.....	23
5.4. Sample Size Justification.....	24
5.5. Data Collection	24
5.5.1 Case Report Form.....	20
5.6. Study Materials.....	25
6. LABORATORY TESTING PROCEDURES	27
6.1. Sample Collection.....	27
6.2. Sample Storage and Handling.....	27
6.3. Testing Algorithm.....	27
6.4. Storage & Shipping.....	30
6.5. Quality Control Testing	30
6.6. Clinical Trial Quality Assurance	31
7. DATA COLLECTION, MANAGEMENT AND REPORTING	33
7.1. Clinical Center Responsibility.....	33
7.2. GenePOC Responsibility	34
7.3. Data Confidentiality	34
7.4. Data Verification and Validation Rules.....	35
8. CLINICAL TRIAL INCIDENTS, RISK MANAGEMENT AND ADVERSE EVENTS	35
9. REGULATORY AND ADMINISTRATIVE INFORMATION.....	37
10. REFERENCES	41
11. APPENDIX.....	42
11.1. APPENDIX A: Clinical Investigation Requirements Relating to Each Clinical Center	42
11.2. APPENDIX B: Testing Algorithm	44
11.3. APPENDIX C: Discrepant Testing Algorithm	45

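### Enrolment may stop on observed performance and its confidence interval, and no sentence confines this to the 150–160 positive window; close on the count instead

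*Combined protocol and SAP*

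**What the plan says.** Two places make the device's own results a ground for closing enrolment. Section 5.4 (Sample Size Justification) says: "The performance obtained and the statistical confidence intervals will be monitored during the study in order to stop the enrollment when deemed appropriate". The Planned Sample Size entry of the Protocol Summary says: "The performance obtained and the confidence interval will be monitored during the study in order to stop the enrollment when appropriate". Neither gives a threshold, a look schedule or an adjustment to the intervals, or says who decides on this ground.

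The target count is stated three ways. Section 5.4 plans to "obtain a minimum of 150 and a maximum of 160 samples positive for GBS based on the Reference Method final result". The Protocol Summary gives a total of 150 with no maximum. Section 5.2.2 aims "to obtain approximately 150 positives samples for GBS based on the Reference Method final result". All three expect up to 600 samples at about 25% prevalence.

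On analysis, the Clinical Study Statistical Methods entry of the Protocol Summary says "The statistical analyses will include all compliant samples and will determine at least the following", and the first item is "The sensitivity and specificity, PPV and NPV as well as exact 95% confidence interval".

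Count-based closure already exists. Section 5.2.2 has the Study Manager follow enrolment and prevalence, and allows a centre to stop early "depending upon the total number of samples and the positive samples obtained across all Clinical Centers". Section 9.7.3 ends a centre's work at an agreed maximum of positives or of samples.

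**The concern.** An exact binomial interval keeps its 95% guarantee when the number of positives is fixed in advance, or at least does not depend on how many the test detected. If enrolment closes because the interval looks good, the sample size depends on the result. The estimate then tends to be high and the interval can miss the truth more often than 5% of the time.

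The influence is practical as well as theoretical. The Study Manager follows enrolment (section 5.2.2) and tells sites during the trial which discrepant samples to ship (section 6.3.3), so disagreement between the methods is visible while enrolment is open. Section 9.7.2 allows the study to be extended if more data are needed for product development. Section 9.7.3 lets the sponsor curtail it if the device needs further development.

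At stake is how the main sensitivity and specificity results can be read. Without a written rule, a reader of the final report cannot tell whether performance played a part in when enrolment ended.

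**Working it through.** **The plan's own figure.** 150 / 0.25 = 600, which reproduces the stated total. The upper end of the range would need 160 / 0.25 = 640. With exactly 600 samples at 25% prevalence, the binomial chance of at least 150 positives is 51.6%; 655 samples give about 90%.

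**Inputs from the documents.** 150–160 reference positives (section 5.4); exact 95% intervals (Protocol Summary), taken as two-sided Clopper–Pearson.

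**Assumptions, because the documents give none.** Enrolment stops at the first look at which the lower 95% limit for sensitivity is at least 90%, and otherwise at the upper end of the range. Looks come after every positive, or after every 10. True sensitivity p runs from 86% to 98%.

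**Method (exact, no simulation).** With x detected among n positives, the lower limit is the 2.5% point of Beta(x, n−x+1) and the upper limit is the 97.5% point of Beta(x+1, n−x). Paths not yet stopped follow P(n, x) = (1−p)·P(n−1, x) + p·P(n−1, x−1). Coverage is the total probability of the stopping points whose interval contains p. Bias is the sum of (x/n) × probability over the stopping points, minus p.

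**Hand check.** At 40 of 40 detected the lower limit is 0.025^(1/40) = 0.912, so the assumed rule would stop there. If true sensitivity is 90%, this has probability 0.9^40 = 1.5%. That single first look already equals the whole 1.4% chance of reaching a 90% lower limit at a fixed 150.

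| Stopping allowed between (positives) | Looks | Lowest coverage | At true sensitivity | Largest upward bias |
|---|---|---|---|---|
| 150 only | none | 95.1% | – | 0 |
| 150–160 | every positive | 95.1% | 86.45% | 0.05 points |
| 40–160 | every positive | 91.0% | 90.0% | 1.0 point |
| 40–160 | every 10 | 92.2% | 90.05% | – |
| 150–300 | every positive | 92.1% | 90.0% | 0.4 points |
| 150–300 | every 10 | 93.0% | 90.1% | – |

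**Chance of a lower limit of 90% or more when the truth is 90%** (looks after every positive): 1.4% at a fixed 150, 2.5% for 150–160, 7.3% for 40–160 and 6.2% for 150–300.

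**Inside the range, other thresholds.** With the threshold set equal to the true value anywhere from 85% to 99%, coverage for 150–160 is still at least 94.6%.

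**How local the shortfall is.** With looks after every positive, the main stretch below 95% is 87.55–90.05% for 40–160 and 88.85–90.0% for 150–300. At a true 90.1% coverage is back to 95.4% and 96.3%. With looks every 10 the shortfall reaches slightly above the threshold, to 91.05% and 90.35%.

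**True sensitivity 95%, 40–160, looks after every positive.** Bias is +1.0 point, 68% of trials close before 150 positives, the mean is 105 positives, and coverage is 98.6%. The cost there is bias and lost sample, not coverage.

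**Stopping on precision instead** (full width 8 or 10 points, assumed; 40–160 positives; true sensitivity 90–97%). The lowest coverage is 94.99%, so the interval is not harmed. If precision closes enrolment well before 150, the estimate still drifts up by less than 1 point.

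**Specificity behaves alike.** At a true 95% with a 95% threshold, stopping between 450 and 480 negatives (three times 150 and 160) gives coverage 95.5%; looking from 90 negatives gives 89.2%.

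**The case against.** The strongest reply is that section 5.4 confines the monitoring already. It sets a minimum of 150 and a maximum of 160 positives under the same heading, so the natural reading is that monitoring only picks the closing point between them. Both damaging cases break a stated limit: 40–160 ignores the minimum, and 150–300 ignores the maximum and would need about 300 / 0.25 = 1,200 samples against up to 600. The 90% threshold and the look schedules are mine. Monitoring an interval may equally mean monitoring its width, which leaves coverage intact. Even a milder breach, 120–160 with looks after every positive, has a lowest coverage of 94.5%.

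Most of this stands, and it limits the severity. It does not remove the point. No sentence links the monitoring to the range, and the Protocol Summary carries the monitoring sentence with no maximum at all. Section 9.7.3 also says that further termination conditions may sit in the Clinical Trial Agreement, which is not among these documents.

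A reader might infer something stronger: that the sponsor plans to stop as soon as the results look favourable, that the reported intervals will therefore be invalid, or that the type I error is inflated. The documents support none of these. They state a minimum of 150. They set no performance goal, hypothesis or significance level, so no error rate can be computed.

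**Conclusion.** The point holds in a limited form. The plan permits results-based stopping and does not confine it to its own 150–160 range, while reporting intervals that assume the stopping point does not depend on results. If stopping stays inside the range, the effect is negligible. If it does not, the reported 95% interval for sensitivity may cover about 91–92% near the level being watched, or early closure may push the estimate up by about 1 point at values well above it. These sizes rest on the assumed 90% rule and on departing from section 5.4's own limits, so the harm is conditional and local. Severity is minor to moderate. It is worth correcting because counts alone are enough to decide when to close.

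**What to change.** Delete the monitoring sentences in the Protocol Summary and in section 5.4, and write instead:

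> Enrolment closes when 150 compliant samples with a positive Reference Method final result and a reportable GenePOC result, whether positive or negative, have been recorded. Closure is decided on counts alone, without reference to agreement between the methods. Samples already enrolled are completed and all compliant ones are analysed. Positives added later by re-testing under section 6.3.2.3 are kept and do not reopen or alter closure.

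Requiring a reportable GenePOC result keeps the count in line with sections 5.3.2 and 6.3.1.1, which leave samples without one out of the analysis.

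As a minimum alternative, state that monitoring may close enrolment only between 150 and 160 reference positives.

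In either case, align the Protocol Summary and sections 5.2.2 and 5.4 on one count, and say whether 600 is a projection or a cap. As a hard cap it would miss 150 positives about 48% of the time at 25% prevalence.

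The cost is wording. Discretionary stopping on performance is given up. If the sponsor did mean to stop early, the forgone saving under the assumed 40–160 rule at a true 95% averages 150 − 105 = 45 positives, or 45 / 0.25 = 180 samples. Samples in progress at closure may take the count somewhat past 160. At 25% prevalence the chance of more than 10 further positives is 34% with 38 samples in progress and 98% with 71. The number in progress is an assumption, so the text should say that 160 is not a cut-off for dropping tested samples.

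A separate item to reconcile: "A potential minimum of 200 samples and a potential maximum of 300 total samples will be obtained at each clinical center". That agrees with 600 for two centres at 300 or three at 200, but gives 800–1,200 if four take part.
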